10.4 Determination of Sample Size

For the sample size calculation SAS version 9.2 has been used.

The primary endpoint of time-to-response of blood markers (defined as time-to-response) is monitored in a survival setting.

Sample Size Calculation The time-to-response of blood markers is monitored in a survival setting. The primary endpoint time-to-response of blood markers comprises recovery of platelets $\geq 150,000/\mu\text{L}$. Accrual period is taken as 1.5 years. Zero to time-to-event period is set at 30 days. As median time-to-response for the control group we take 6 days (this information is calculated based upon Bandarenko et al.²⁸). For the treated group with ALX-0081 we assume a 44% risk reduction corresponding to a reduction in median time to event of 2.64 days, and ultimately resulting in a time-to-response of 3.36 days. The hazard ratio is defined in the SAS code as the hazard of control versus experimental (ALX-0081) treatment thus equalling to $6/3.36=1.786$. The sample size calculations are performed based on a log-rank test, aiming for a power of 80%, tested 1-sided at 2.5% significance level with 1:1 randomisation. Note that we assume that 15% of subjects would be lost-to-follow-up. The latter is justifiable because the active follow-up period only equals 30 days. Based on the above described assumptions a sample size of 110 subjects is required.

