Complete remission: Complete remission is defined as recovery of platelets (confirmed by platelets  $\geq 150,000/\mu\text{L}$  and LDH  $\leq 2 \times \text{ULN}$  at 48 hrs after initial platelet response) and absence of exacerbation.

Initial platelet recovery: Date of initial platelet recovery is defined as the first occurrence of platelets  $\geq 150,000/\mu\text{L}$  which is **confirmed** 48 hours later by platelets  $\geq 150,000/\mu\text{L}$  and LDH  $\leq 2 \times \text{ULN}$ . For example, if platelets reach  $\geq 150,000/\mu\text{L}$  on Day 5, are not confirmed at Day 7, reach  $\geq 150,000/\mu\text{L}$  again on Day 10 and are confirmed at Day 12, the initial platelet recovery occurs on Day 10. Initial platelet recovery and confirmation dates will be determined using the actual lab results, following standardisation to consistent units.

Time to Response: Time to response will be calculated as the number of days, hours and minutes (represented by number of days with two significant digits after the decimal point) from study drug administration to initial platelet recovery, as defined above. An

---

observation is censored if the observation does not meet the defined time interval of 30 days, due to any cause of loss-to follow-up (including death), or endpoint not being reached.

Subjects that attain confirmed platelet response:

Time-to-Response = [Date and time (hrs, min) of initial platelet recovery] – [Date and time (hrs, min) of first study drug administration]

Exacerbation: Exacerbation of TTP is defined as recurrent thrombocytopenia following a confirmed platelet response and requiring a re-initiation of daily PE treatment  $\geq 1$  day but  $\leq 30$  days after the last daily PE.

Relapse: Defined as de novo event of TTP that occurs later than 30 days after the last daily PE.

First PE: Defined as start of PE.

First on-study PE: Defined as first PE received after randomisation.

In case first on-study PE is not first PE, then first on-study PE should be started within 24 hours (after the end) of the first PE. If not it is considered major protocol deviation.

Overall duration of study treatment exposure (days): Defined as date of last dose of study treatment – date of first dose of study treatment + 1

Duration of study treatment exposure during daily PE (days): Defined as date of last dose of study treatment during the daily PE period – date of first dose of study treatment during the daily PE period + 1

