### 6.1.4 Determination of Sample Size

The primary endpoint of time-to-response of blood markers (defined as time-to-response) is monitored in a survival setting. The time-to-response of blood markers comprises recovery of platelets  $\geq 150,000/\mu\text{L}$ . Accrual period was taken as 1.5 years. Actual accrual time is longer than 1.5 years; however there is no impact on the sample size. Zero to time to event period is set at 30 days. As median time-to-response for the control group we take 6 days (this information is calculated based upon Bandarenko *et al.*). For the treated group with ALX-0081 we assume a 44% risk reduction corresponding to a reduction in median time to event of 2.64 days, and ultimately resulting in a time-to-response of 3.36 days. The hazard ratio is defined in the SAS code as the ratio of control versus experimental (ALX-0081) treatment thus equaling to  $6/3.36=1.786$ . The sample size calculations are performed based on a log-rank test, aiming for a power of 80%, tested 1-sided at 2.5% significance level with 1:1 randomisation. Note that we assume that 15% of subjects would be lost-to-follow-up. The latter is justifiable because the active follow-up period (time of first study drug administration to time to event) only

---

equals 30 days. Based on the above described assumptions a sample size of 110 adult subjects is required. As subjects can be replaced, the ITT population may be larger than 110 subjects.

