### *Sensitivity analyses with regards to primary (and secondary) efficacy endpoints*

Sensitivity analyses comprise the following aspects:

- 1) For efficacy endpoints (EPs) (primary and secondary), analyses performed on per protocol (PP) populations. Details on major deviations are specified in [Appendix II](#).
- 2) Analysis of treatment effect adjusted for the following covariates:
  - a. ADAMTS13 activity at baseline: < 5% vs.  $\geq$  5%,
  - b. von Willebrand Factor (vWF) level (continuous),
  - c. first episode vs. recurrent disease (as described in [Section 6.2.4](#)),
  - d. Ristocetin Cofactor (RICO) suppression < 20% throughout treatment period: yes vs. no,
  - e. absence/presence of one PE session prior to randomisation.

A Cox proportional hazards model is fit to the data, and in addition to treatment, significant (5% significance level; SL) covariates are retained. This will be represented by means of Forest plots for the covariates found to be significant.

- 3) Analysis of non-confirmed and confirmed platelet response (instead of confirmed platelet response only) for the ITT population: see **Table 2**, with changes to
- 4) **Table 1** indicated in **bold green**.
- 5) Assessment of impact (potential bias) of use of rituximab during daily PE: log rank analysis of primary endpoint with subjects censored at time they start using rituximab for the ITT population. Use of rituximab will be determined by using the Concomitant Medications data (both PE related and not PE related) with ATC code “L01XC” (coded term “RITUXIMAB”).

**Table 2: Censoring/event scenarios (for ITT and PP analysis of non-confirmed and confirmed platelet response; changes to Table 1 indicated in bold green)**

Case	Description	Time at risk/ Time to recovery of platelets (days)	Responder	Censored (No = 0; Yes = 1)
1	No event in 30 days of continuous daily PE a	30	No	1
2	At day 30, confirmed recovery of platelets (per protocol)	30	Yes	0
3	At day x b (1 st measurement of platelet recovery), confirmed recovery of platelets, ideal case (per protocol)	x	Yes	0
4	No event occurred and subject is no longer in trial at day x b (including replaced subjects who are dosed)	x	No	1

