5	At day xb (1st measurement of platelet recovery), subject has recovery of platelets, however, missing data at 48 hours later, and no subsequent confirmation on platelet count during daily PE (no more daily platelet measurements)c	x	Yes	0
6	No recovery of platelets, however daily PE stopped (daily PE considered surrogate for responsed). Except if PE stopped due to AEe (then idem case 4)	Time of last daily PE	Yes	0
7	Subject not dosed (after randomisation)	1	No	1

a PE = plasma exchange.

b At day x within 30 days assessment period.

c No subsequent confirmation during daily PE, since daily PE has been stopped by Investigator for clinical response which does not meet protocol definition of response.

d Certain subject's platelet counts 'hover' around 150,000/ $\mu$ L and in clinical practice PE is stopped.

e Start and stop dates of adverse events related to PE will need to be compared to PE stop dates in order to identify PE stopped due to AE.

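### SAP Table 2, the sensitivity analysis for non-confirmed platelet response, relaxes missing confirmation and PE stop but never counts a failed 48-hour re-test at its own date

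*SAP*

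**What the plan says.** The primary event is a platelet count of at least 150,000/µL, confirmed 48 hours later by two conditions together: platelets still at or above the cut-off, and LDH no more than 2 × ULN (SAP 6.3.1, Censoring and event plan). A re-test can therefore fail on platelets or on LDH alone.

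SAP 3 gives a worked example of a failed re-test. The cut-off is reached on Day 5 and not confirmed on Day 7. It is reached again on Day 10 "and are confirmed at Day 12, the initial platelet recovery occurs on Day 10".

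Sensitivity item 3 is described as an "Analysis of non-confirmed and confirmed platelet response (instead of confirmed platelet response only) for the ITT population", and Table 2 lists its censoring and event rules. Case 5 covers a measured recovery with "missing data at 48 hours later, and no subsequent confirmation on platelet count during daily PE"; it becomes an event at day x. Case 6 covers a subject with no recovery whose daily PE is stopped for a reason other than an adverse event; it becomes an event at the last daily PE. A footnote to Case 6 explains that some subjects' counts hover near the cut-off and PE is stopped in practice. Case 1, "No event in 30 days of continuous daily PE", stays censored at 30. Cases 2, 3, 4 and 7 are also as in Table 1.

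**The concern.** The plainest meaning of a non-confirmed response is a recovery whose re-test was done and did not pass. The SAP foresees such subjects in its own example, yet neither table has a row for them, and nothing in Table 2 dates an event at a first count that failed its re-test. The LDH condition is never explicitly relaxed for a completed re-test.

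This matters because item 3 is the only planned time-to-response analysis that relaxes confirmation at all. The per-protocol, covariate-adjusted and rituximab-censored analyses keep the rule. SAP 6.3.2 does report platelets regardless of confirmation, but as a proportion at two fixed visits. If Table 2 agreed with the primary result, a report could present that as robustness to the confirmation rule, although the failed re-tests had been left as they were or handled by an unstated convention.

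**Working it through.** **1. The plan's own figure.** Inputs from SAP 6.1.4 and Protocol 10.4: "aiming for a power of 80%, tested 1-sided at 2.5% significance level with 1:1 randomisation"; "As median time-to-response for the control group we take 6 days"; hazard ratio 6/3.36 = 1.786; "we assume that 15% of subjects would be lost-to-follow-up"; "Zero to time-to-event period is set at 30 days".

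Schoenfeld events = 4 × (1.960 + 0.842)² / (ln 1.786)² = 93.4. Dividing by 0.85 gives 109.9, so N = 110 is reproduced. Nothing below changes it.

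**2. Table 1 against Table 2.**

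| Case | Situation | Table 1 | Table 2 |
|---|---|---|---|
| 1 | 30 days of daily PE, no event | censored at 30 | same |
| 2, 3 | confirmed recovery | event at 30 or x | same |
| 4 | left the trial, no event | censored at x | same |
| 5 | recovery, 48-h value missing, no later confirmation | censored at x | event at x |
| 6 | no recovery, daily PE stopped (not for an AE) | censored at last daily PE | event at last daily PE |
| 7 | not dosed | censored at 1 | same |

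**3. Where a completed but failed re-test goes under Table 2.**
- A later recovery is confirmed: event at the later date (Case 3 with the SAP 3 rule), as in Table 1.
- Daily PE continues to day 30 with no confirmation: censored at 30 (Case 1), as in Table 1.
- The subject leaves the trial: censored at that day (Case 4), as in Table 1.
- Daily PE is stopped: Case 6 applies only if its lack of recovery means lack of *confirmed* recovery. The date is then the last daily PE, not the first count.

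**4. The SAP's example.** Table 1 gives Day 10 and Table 2 gives Day 10. An analysis that counts the non-confirmed response gives Day 5.

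**5. How many subjects could be involved.** The documents give no re-test failure rate, so the rates here are assumptions. With exponential times, 55 per arm and no loss, the number reaching the cut-off within 30 days is 55 × (1 − 2^(−30/6)) + 55 × (1 − 2^(−30/3.36)) = 53.3 + 54.9 = 108.2. If 5%, 10%, 20% or 30% of first recoveries fail a completed re-test, that is about 5, 11, 22 or 32 subjects.

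**6. Effect on the hazard ratio, illustrative only.** Exponential times were simulated with the planned medians and 30-day censoring. A failed re-test was assumed to delay the confirmed date by 5 days. Dated at the first count, the HR is 1.79. Dated by Table 2:

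| Failure rate, placebo / ALX-0081 | 30% of failures never confirm and stay at risk to day 30 | All failures confirm later | 30% never confirm but become Case 6 events 3 days after first count |
|---|---|---|---|
| 10% / 10% | 1.58 | 1.76 | 1.80 |
| 20% / 20% | 1.48 | 1.77 | 1.73 |
| 10% / 20% | 1.33 | – | 1.65 |
| 30% / 10% | 2.00 | – | – |

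A dash means not run. Simulation error is about 0.03 in the last two columns. With equal failure rates, nearly all of the shift comes from keeping never-confirmers at risk to day 30. With unequal rates the HR can move in either direction.

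**The case against.** The best defence is that Table 2 answers a coherent question of its own. Its footnotes aim at subjects whose PE was stopped for a clinical response that missed the protocol definition. Case 5 does relax the rule where confirmation is missing. Case 6 can take in some failed re-tests: SAP 3 defines initial platelet recovery as a confirmed one, so a subject who touched the cut-off, failed the re-test and then stopped PE may be classed as having no recovery and counted as an event. The footnote about hovering counts fits that subject. Counting the first qualifying count whatever follows is also a different estimand, because it accepts transient rises.

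Most of this stands, and it rules out two stronger readings. A reader might infer that Table 2 does not test the confirmation rule at all, or that it leaves every failed re-test exactly as in the primary analysis. The documents support neither, because of Cases 5 and 6.

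The defence does not close the gap. The Case 6 route depends on a meaning the SAP does not fix: the censoring and event plan takes the first time at the cut-off as the time of recovery, which points the other way. Two programmers could code the same subject as an event or as censored. Even on the generous reading the date is the last daily PE, and the routes through Cases 1, 3 and 4 are unchanged. An analysis limited to missing confirmation and PE stop would be legitimate, but item 3 does not describe itself that way.

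**Conclusion.** The point holds as a mismatch between the analysis named in item 3 and the rows that implement it. Agreement between Tables 1 and 2 would say nothing about robustness to failed re-tests that stay under Cases 1, 3 or 4.

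The row comparison and the Day 10 against Day 5 result follow from the text alone. The size does not: the subject counts and hazard ratios rest on assumed failure rates, delays and never-confirm fractions, so they show possible scale and direction and are not a forecast. It is tempting to set the example's 5-day shift against the planned 2.64-day difference, but one illustrative subject's delay is not comparable with a difference in arm medians.

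One sensitivity analysis is affected. It should be corrected before the analysis is programmed; it does not threaten the primary conclusion.

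**What to change.** In Table 2:
- Define the event for every dosed subject as the first platelet count of at least 150,000/µL within 30 days of first dose, timed at that count, whether the 48-hour re-test passed, failed or is missing.
- Add a row: recovery measured, 48-hour re-test done and failed; time x; responder yes; censored 0. Identifying platelet and LDH failures separately would show which condition matters.
- Reword Cases 1 to 5 to match, including Case 4 for a subject who fails a re-test and then leaves the trial.
- Limit Case 6 to subjects who never reached 150,000/µL.
- Settle the population: item 3 names ITT only, while the Table 2 title names ITT and PP.

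If the team wants only missing confirmation and PE stop examined, the minimum is to rename item 3 accordingly and state how a failed re-test is coded.

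The cost is SAP wording and one reprogrammed analysis. Platelets and LDH are already scheduled daily during daily PE (Protocol 8.1.2), so no new data are needed. The downside is that transient rises count as response, in this sensitivity analysis only.

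### In the Table 2 sensitivity analysis, Case 6 can score a stop of daily PE for a non-PE-related adverse event as a platelet response, and its overlap with Case 4 is left unresolved

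*SAP*

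**What the plan says.** SAP 6.3.1 gives two coding tables. Table 1 governs the primary analysis of confirmed response. Table 2 serves sensitivity item 3, which also admits unconfirmed response. The entries that matter here are:

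- **Case 6:** "No recovery of platelets, however daily PE stopped (daily PE considered surrogate for response"). The time is that of the last daily PE. Table 1 codes it as a censored non-responder; Table 2 codes it as a responder with an event.
- **Exception within Case 6:** "Except if PE stopped due to AE", in which event the subject is handled as Case 4.
- **Footnote e**, on how to find the exception: "Start and stop dates of adverse events related to PE will need to be compared to PE stop dates".
- **Footnote d**, on the reason for Case 6: some counts stay close to 150,000/µL and PE is stopped in practice.
- **Case 4**, the same in both tables: no event and the subject has left the trial; non-responder, censored.

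The Time to Response definition in SAP section 3 and the censoring plan in 6.3.1 both name death as a reason for censoring.

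**The concern.** The exception and its footnote do not match. The exception covers any AE; the footnote's search covers PE-related AEs only. Protocol 9.1.1 counts worsening of existing disease, and lack of efficacy in acute treatment of a life-threatening disease, as AEs. SAP 6.4.1 tabulates TTP-related and PE-related AEs as separate categories. Followed as written, footnote e misses AEs that signal failure rather than response, unless they are also flagged as PE-related.

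The second gap is precedence. A subject who dies or withdraws during daily PE without recovery fits both Case 4 and Case 6. In Table 1 both are censored, so the overlap affects only the censoring time. In Table 2 it decides between event and censoring.

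Item 3 is the only time-to-event sensitivity analysis that relaxes the confirmation rule, so it will be read as support for, or a challenge to, the primary result. The investigator knows the allocation (protocol 7.5), and stopping daily PE follows site practice and clinical judgement (protocol 4.3 and 7.1). The frequency of such stops could therefore differ between arms.

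**Working it through.** **Coding logic.** Subjects without platelet recovery, taken through the rules as written:

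| Situation when daily PE stops | Rules met | Table 1 | Table 2 |
|---|---|---|---|
| On study, count near 150,000/µL, PE stopped in practice | Case 6 | censored | event (intended) |
| On study, PE-related AE | Case 6 exception, found by footnote e | censored | censored |
| On study, other AE, including TTP worsening or lack of efficacy | Case 6 exception by its text, not found by footnote e | censored | event |
| Died or withdrew | Case 4, and also the wording of Case 6 | censored | censored or event; no precedence |

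The third row contradicts footnote d. The fourth is an ambiguity.

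**The plan's own figure.** Inputs from SAP 6.1.4:

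- "tested 1-sided at 2.5% significance level with 1:1 randomisation"
- "aiming for a power of 80" per cent
- "As median time-to-response for the control group we take 6 days", against 3.36 days on ALX-0081, so the hazard ratio is 6/3.36 = 1.786
- "15% of subjects would be lost-to-follow-up"
- "Zero to time to event period is set at 30 days"

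Schoenfeld events = (1.960 + 0.842)² / (0.25 × (ln 1.786)²) = 93.4. Dividing by 0.85 gives 109.9, so the stated 110 is reproduced. It does not depend on the Case 6 rule.

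**Size of the coding effect (illustration).** The shares of subjects with a Case 6 stop that is really a failure are assumptions. Let s be the share whose PE stops before recovery, with constant hazards. If the response hazard is λ, the stop hazard is λs/(1 − s) and their sum is λ/(1 − s). Coding stops as responses therefore gives

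apparent hazard ratio = true hazard ratio × (1 − s_placebo)/(1 − s_ALX).

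Simulation: 55 per arm, exponential times, 30-day window, unstratified log-rank test at one-sided 2.5%, 8,000 trials per row. The Monte Carlo standard error near 2.5% is √(0.025 × 0.975/8,000) = 0.2 percentage points.

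No true effect (median 6 days in both arms); rejection in favour of ALX-0081:

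| Stops, placebo / ALX-0081 | Apparent hazard ratio by formula | Stops censored | Stops coded as responses |
|---|---|---|---|
| 10% / 10% | 1.00 | 2.4% | 2.8% |
| 5% / 10% | 0.95/0.90 = 1.06 | 2.9% | 4.9% |
| 10% / 20% | 0.90/0.80 = 1.13 | 2.7% | 9.5% |
| 10% / 30% | 0.90/0.70 = 1.29 | 2.7% | 25.3% |

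The direction follows the imbalance. With 20% on placebo and 10% on ALX-0081 the formula gives 0.80/0.90 = 0.89, which works against ALX-0081.

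Planned effect (6 against 3.36 days), equal shares in both arms:

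| Stops per arm | Power, stops censored | Power, stops coded as responses | Mean number recoded, of 110 |
|---|---|---|---|
| 0% | 84% | 84% | 0 |
| 10% | 80% | 85% | 11 |
| 20% | 76% | 85% | 22 |
| 30% | 70% | 85% | 33 |

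With equal shares the hazard ratio stays at 1.786. Power rises only because failures are added to the event count.

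**The case against.** The strongest reply is that the SAP already says what it means. The exception in Case 6 is not limited to PE-related AEs, and footnote e could be read as a note on date matching. Case 6 calls stopping PE a surrogate for response, and footnote d shows that it targets clinical responders who narrowly miss the definition. This stands as evidence of intent. It does not settle the coding, because footnote e is the only operational instruction and it is narrower than the rule it serves.

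A reader might infer that Table 2 scores deaths as responses. The documents do not support that. Case 4 is kept in Table 2, a subject who has died has left the trial, and the SAP twice names death as censored. Censoring is the natural reading; what is missing is a line saying that Case 4 comes first.

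A reader might also apply the 10% to 30% mortality in protocol 2.5.2 to 55 per arm and expect 5.5 to 16.5 miscoded deaths. That figure is mortality of an acute idiopathic episode, not deaths on daily PE before recovery, and those deaths belong to Case 4. Nor does any document point to an excess of failures on ALX-0081, which the inflated rejection rates need.

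The reply is also right on scope. Deaths are tabulated by arm and period in SAP 6.3.2, so an excess would be seen. The same section summarises platelet counts of at least 150,000/µL without requiring confirmation, though as a proportion and not as time to event.

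**Conclusion.** The point holds in a limited form. As instructed, Table 2 turns a PE stop for a non-PE-related AE in a subject still on study into a response, and it leaves the Case 4 and Case 6 overlap open where that overlap now matters. Any false-positive bias depends on imbalance between arms. With equal shares there is little or none, although apparent power under the planned effect rises (85% against 76% at 20% stops per arm). With 10% against 20% and no true effect, rejection is 9.5% instead of 2.7%. These sizes rest on assumed shares, constant hazards, and every such stop being a failure; the number of Case 6 subjects is not known from the documents. Only one sensitivity analysis is affected. The primary analysis, where Case 6 is censored, and the sample size of 110 stand. The wording should be corrected before database lock.

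**What to change.** In SAP 6.3.1, Table 2:

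1. State that Case 4 takes precedence over Case 6 for death, withdrawal or any other departure from the trial.
2. Amend footnote e so that PE stop dates are compared with all AEs, including TTP-related AEs and lack of efficacy, not only those related to PE.
3. Limit Case 6 to subjects alive and on study with no such AE at the PE stop.
4. List each Case 6 subject with the last platelet count and any recorded reason for stopping.

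The cost is a few lines of SAP text. AE dates, deaths and PE session times are already collected. A few more subjects will be censored, and the listing needs some review: protocol 8.2.1.1.1 asks for a reason when a single session is interrupted, not for ending the PE course. PE abandoned for lack of effect with no AE recorded would therefore still reach Case 6, and the listing is what would reveal it.
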